We hypothesize that intermittent stimulation of either the right or left human hemidiaphragm during thoracic surgical procedures and lung transplant lasting approximately 5 hours or longer will prevent or attenuate inactivity-induced changes in gene expression, mitochondrial function and single fiber contractile properties as compared to the unstimulated hemidiaphragm.

6. Research Plan:

Subjects:

Patients undergoing regularly scheduled cardiothoracic surgery, including lung transplants, at Shands Hospital at the University of Florida will be recruited to enroll in this prospective study. From each subject an informed consent will be obtained to donate two diaphragm muscle biopsy samples during the surgery.

After recruitment, an initial evaluation consisting of basic demographic information as well as diagnostic information pertaining to the surgery will be performed before the scheduled surgery to search for exclusion factors. In addition, we will track medications, ventilator use, complications, and length of stay during the patient's hospitalization for surgery. Up to 100 subjects will be studied.

Exclusion Criteria:

1. Age < 18 or > 80,
2. history of prior surgery to the diaphragm or pleura;
3. a diagnosis of COPD will be determined from a clinical history consistent with chronic bronchitis and/or emphysema, a long history of cigarette smoking, and pulmonary function tests consistent with irreversible airflow obstruction (FEV1 < 40% predicted, according to European Respiratory Society criteria (1)).
4. a diagnosis of chronic heart failure (NYHA class IV) (2)
5. clinical diagnosis of other lung disease (cystic fibrosis, bronchiectasis, lung cancer; etc.);
6. renal insufficiency (serum creatinine > 1.6 mg/dl);
7. severe hepatic disease (any liver function tests > 1.5 times the upper limit of normal);
8. undernourishment (body mass index < 20 kg/m²),
9. chronic uncontrolled or poorly controlled metabolic diseases (e.g., diabetes, hypo- or hyperthyroidism)
10. orthopedic diseases, suspected paraneoplastic or myopathic syndromes,
11. if in the surgeons' judgment the patients' clinical status warrants, diaphragm stimulation will be stopped and biopsies will not be obtained,
12. items #3 and #5 above will not apply to transplant patients.

Experimental Procedure:

Before the surgery:

A pulmonary function test will be performed to determine whether the subject qualifies for the study.

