PFT: Subjects will complete a forced expiratory maneuver to determine eligibility for training. Tests will be completed according to American Thoracic Society guidelines,(3) and 3 to 5 trials administered, separated by 2 minutes of rest. If an individual demonstrates FEV1<40% of predicted, he or she will be removed from any further

participation in the study. An FEV_{1.0} of 40% or less of predicted as an exclusionary factor will not apply to transplant patients.

In addition, the qualified subjects will undergo maximum inspiratory pressure test before the scheduled surgery.

Maximal Inspiratory Pressure: Subjects will perform a maximal inspiratory pressure maneuver from residual volume, in accordance with American Thoracic Society testing guidelines.(3) Trials will be administered until 5% variability is achieved between three trials (typically achieved within 5 trials), and separated by a two-minute rest. A short rest between maneuvers will be provided to prevent muscle fatigue.

In conjunction with respiratory testing, we will monitor baseline and exertional blood pressure, heart and respiratory rate, and pulse oximetry. The following tests will be completed on all subjects.

During surgery following procedures will be performed,

Diaphragm stimulation: Either the right or the left hemidiaphragm will be stimulated during routine cardiothoracic surgical procedures. This will be decided by the surgeon on the basis of ease of access to the corresponding phrenic nerve. Rodent models of MV have shown that different neuromuscular blockers can exert varied effects on the diaphragm contractile properties (4-7). The right or the left hemidiaphragm will be stimulated via the corresponding phrenic nerve with a temporary cardiac pacer (Medtronic 5388) with wire electrodes. The surgeon will identify the phrenic nerve on the pericardium and the pacing electrodes will be sutured to the pericardium immediately adjacent (~8 mm) to either side of the phrenic nerve (8). It is not necessary for the pacing electrodes to touch the phrenic nerve to stimulate the phrenic nerve and generate a hemidiaphragm contraction.

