Our model is not a pure MV inactivity paradigm with the addition of surgery, but it is not possible to ventilate humans and obtain diaphragm biopsies for experimental purposes, as is possible with animal models. Our surgery/MV model, however, is the actual clinical situation that often leads to VIDD and difficult weaning in humans, and thus, our results will be highly relevant to the clinical management of these patients.

Data safety monitoring board:

A data safety monitoring board comprised of three physicians will be impaneled before any additional subjects are studied. Prior to collecting additional data, the panel will be convened to review the study protocol, safety measures and establish operating policies. The data safety monitoring board will meet at least annually and will be given immediate reports of any serious and unexpected adverse events that may occur. DSMB findings and reports will be included in the annual renewal of this protocol to the IRB.

Diaphragm Biopsies:

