mg/ml NTB (nitrotetrazolium blue). Complex II: 4.5 mM EDTA, 10 mM KCN, 0.2 mM phenazine methasulfate, 84 mM succinic acid and 50 mM NTB in 1.5mM phosphate buffer, pH 7.4. Complex IV: 5 mg 3:30-Diamidobenzidine tetrahydrochloride (DAB) dissolved in 9 ml phosphate buffer (0.05 M, pH 7.4), 1 ml catalase (20 µg/ml), 10 mg cytochrome c, and 750 mg sucrose. Complex V: 35 mM Tris, 270 mM glycine, 14mM MgSO₄, 0.2% Pb(NO₃)₂, and 8 mM ATP, pH 7.8. Gels will be washed in distilled water and the bands quantified by digital imaging using a CCD camera. Activity and content will be normalized to muscle weight, mitochondrial DNA content (21) as well as citrate synthase activity (22).

3. Titan analysis: The integrity and phosphorylation of Titan subunits of the sarcomere will be analyzed in [name] laboratory at the University of Arizona. [name] group has extensive experience making this unique measurement and will follow procedures as they have previously published.(25, 26)

Statistical Analysis:

We will use a mixed effects model with random intercept for each subject to evaluate the fixed effects of stimulation and fiber type on single-fiber force mechanics. For other dependent variables (i.e. mitochondrial respiration, RNA, protein quantification), we will test differences between the stimulated and unstimulated tissue samples using paired parametric T tests when the data meet the assumptions of parametric analysis, or non-parametric tests if the data are not normally distributed.

7. Possible Discomforts and Risks:

The risks of diaphragm biopsy include failure of the biopsy site to close, bleeding, phrenic nerve injury, and diaphragm dysfunction. The portion of the diaphragm from which the biopsy is obtained (6 mm by 20 mm section of tissue) will be isolated from the remaining muscle by surgical staples, prior to excision of the full-thickness biopsy sample. The site will also be reinforced with sutures, minimizing the risks of bleeding or failure of the biopsy site to close.

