While human diaphragm biopsies are a relatively new model to study muscle, numerous workers have obtained non-therapeutic, experimental human diaphragm tissue samples during routine surgeries, as proposed in this work (27-35) and no complications were reported. We have recently completed a study in which two diaphragm samples were obtained from 5 subjects at the beginning and end of CT surgery, and there were no intra or postoperative complications associated with the diaphragm biopsies. The addition of indirect phrenic nerve stimulation to the protocol poses no significant risk to the subjects.

Respiratory testing (pulmonary function testing & maximum inspiratory pressure testing) may elicit transient fatigue or shortness of breath that resolves within several seconds of completion. Each training set typically lasts less than 15 seconds, and at least two to three minutes of rest will be provided between trials to minimize feelings of exertion, and perceived exertion will be monitored during training sessions.

This study may include risks that are unknown at this time.

8. Possible Benefits:

There are no direct benefits to the subjects for participating in this study, but our results will lead to a better understanding of how MV affects human diaphragm and may lead to improved clinical care for MV patients. The potential importance of optimizing diaphragmatic function prior to surgery was shown by Hulzebos (2006). These researchers showed that 2 weeks of specific diaphragm training prior to coronary bypass surgery significantly reduced the incidence of post operative pneumonia and duration of hospitalization. The molecular basis of the improved post-operative diaphragmatic function following preoperative conditioning is unknown.

9. Conflict of Interest:

No real or potential conflict of interest exists for any investigator with regard to this research project.

Reference:

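### Complications are tracked only during the surgical admission, so the window varies with length of stay and biopsy-related events first recognised after discharge would not be actively collected

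*Combined protocol and SAP*

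**What the plan says.** Section 6 (Subjects) sets the period for collecting clinical events: "we will track medications, ventilator use, complications, and length of stay during the patient's hospitalization for surgery". The same paragraph gives the sample size: "Up to 100 subjects will be studied".

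Section 7 lists what could go wrong: "The risks of diaphragm biopsy include failure of the biopsy site to close, bleeding, phrenic nerve injury, and diaphragm dysfunction". The tissue is a full-thickness sample of about 6 mm by 20 mm from each hemidiaphragm (section 6, Diaphragm Biopsies). Section 8 says that subjects gain no direct benefit.

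Both respiratory tests come before the operation. For spirometry: "A pulmonary function test will be performed to determine whether the subject qualifies for the study". For inspiratory strength: "In addition, the qualified subjects will undergo maximum inspiratory pressure test before the scheduled surgery". The heading C. After Surgery leads directly into laboratory methods and then the statistical analysis. It describes no visit, call, test or record review.

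A three-physician data safety monitoring board is planned. It meets at least annually and "will be given immediate reports of any serious and unexpected adverse events that may occur".

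As prior evidence of safety, section 7 cites published biopsy work and the group's own study, in which "two diaphragm samples were obtained from 5 subjects at the beginning and end of CT surgery" and no biopsy-related complications were seen. It does not say how long those subjects were followed or how complications were looked for.

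**The concern.** The biopsies are non-therapeutic and bilateral, so the record of harm is an important product of the study even though it is not an aim. As written, the period of observation is not the same for everyone. It ends when the subject goes home, and length of stay is itself one of the items tracked in that sentence. The study mixes routine cardiothoracic cases with lung transplants, so there is no reason to expect a common length of observation.

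At least some of the named risks could come to light after discharge, for example a biopsy site that fails later, or weakness noticed only when the patient is more active. Nothing in the plan would actively find these. The investigators already rely on an absence of complications in an earlier small series to support this study. A similar statement made at the end of this one would be read as covering recovery as a whole, when the data behind it would stop at discharge.

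**Working it through.** The plan gives no complication rate, length of stay, definition of a complication or safety sample-size calculation, so there is no figure of its own to reproduce. The check is mainly a comparison of sections.

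**1. What is observed, and when**

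- Before surgery: spirometry for eligibility, and maximal inspiratory pressure (section 6, Before the surgery).
- Surgery to discharge: medications, ventilator use, complications and length of stay (section 6, Subjects).
- After discharge: no scheduled collection (section 6, C. After Surgery).
- No stated end date: immediate reports to the safety board, limited to events that are both serious and unexpected (section 6, Data safety monitoring board).

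**2. The four named risks against those channels**

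- Evident during the admission: collected as a complication or reflected in ventilator use. This applies to all four.
- First recognised after discharge: not actively collected. It could reach the safety board only if someone reported it and it was judged serious and unexpected. Because section 7 already names all four, they may not count as unexpected.
- Side of the event: not recorded, although one side is stimulated and the other is not.

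**3. What a zero count could support**

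For zero events in n subjects, the exact one-sided 95% upper limit is 1 − 0.05^(1/n).

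- Earlier series, n = 5: 1 − 0.05^(1/5) = 0.451, or 45.1%.
- This study at its maximum, n = 100: 1 − 0.05^(1/100) = 0.0295, or 3.0%.

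The second limit applies to the rate of events that the plan would record. If a share s of all events is recorded, the limit on the true rate is 0.0295/s. Since s cannot exceed 1, 3.0% is the most favourable value. The documents give no basis for choosing s, so none is used here.

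**The case against.** The strongest reply is that this is a mechanistic tissue study. Aims 1 to 3 and the statistical analysis concern the paired muscle samples. No complication rate, counting rule or safety claim is planned, and no result in the aims changes with the length of follow-up. All of that stands. It makes this a point about safety ascertainment and not about validity.

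Several stronger readings are tempting, and the documents do not support them.

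- A reader might infer that inpatient tracking is all the safety oversight there is. The safety board also reviews safety measures and sets its operating policies before further data are collected, and its reporting has no stated end at discharge. It is a narrow channel, but it exists.
- A reader might infer that uncollected events would be counted as absent in a biased rate. No rate is planned. The point bears only on what a later summary could claim.
- A reader might infer that some of the named risks are not observed at all. Any of the four that is clinically evident in hospital would be captured, including weakness that prolongs ventilation.
- A reader might infer that observation is shortest for those most at risk. A subject with respiratory impairment may well stay longer and be watched longer. The window varies, but the direction of any distortion is not established.
- A reader might note that "the qualified subjects will undergo maximum inspiratory pressure test before the scheduled surgery", with no later value, and ask for a repeat test. Every subject is biopsied on both sides and there is no unbiopsied group, so a fall in pressure could not be separated from the effect of surgery. The test also cannot assign a side. A repeat is not part of this point.

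Finally, the consent pages are not in the public text, so post-discharge contact described there cannot be ruled out.

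**Conclusion.** The point holds as a limited one. Complication tracking ends at discharge, the window differs between subjects, and biopsy-related events first recognised later would not be actively collected. A statement of no complications from this study would cover the inpatient period only. The paired tissue comparisons are untouched.

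How many events would be missed cannot be said, because the share first recognised after discharge is not in the documents and no figure for it is assumed. The conclusion rests on two readings: that the wording in section 6 (Subjects) limits complications, as well as the other items, to the admission; and that no follow-up is set out elsewhere, such as in the consent form. It is a low-cost improvement that the sponsor should make, not a flaw that undermines the study.

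**What to change.** In section 6 (Subjects), separate complications from the other tracked items and give them one window of a stated number of days from surgery, the same for all subjects. Thirty days is an example. Where a stay is longer, collection can run to discharge, but events should be reported for the common window so that every subject contributes the same period. A window ending at the first clinic visit would not serve, because the documents do not fix that date and it may differ between subjects.

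Take the information from hospital and routine follow-up records, including known readmissions. Record each of the four risks in section 7 as present, absent or not assessed, so that a missing record is not read as a negative one. Where a side applies, record whether it was the stimulated or unstimulated one. The surgeon chooses the side by ease of access, so a comparison of sides would be descriptive. Send the summary to the safety board with its regular review.

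The cost is modest chart review per subject and a short form. No new visit or procedure is needed. Readmissions to other hospitals would be captured incompletely, and the complication figure may be less favourable than an inpatient-only count.

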Protocol

1. Project Title:

The effect of hemidiaphragm stimulation during surgery on gene expression and single fiber contractile properties in humans

2. Investigator(s):

[name], PT;
[name], MPH

3. Abstract:

Approximately 10% of the patients who receive mechanical ventilation (MV) experience difficulty weaning, and these patients account for approximately 40-50% of the total MV days. Numerous animal studies have documented that MV induced muscle inactivity leads to diaphragm atrophy, oxidative stress, altered diaphragm gene expression and reduced muscle strength in as little as 6-24 hours. This phenomenon has been termed ventilator induced diaphragm dysfunction (VIDD). Spontaneous breathing for 5 minutes every 6 hours over a 24 hour period of MV support can attenuate VIDD by approximately 50% in a rodent model, indicating that very brief periods of normal diaphragm activity can be protective. Recent human work has documented VIDD (diaphragm muscle fibers atrophying ~ 55%) following approximately 39 hours of controlled MV. Clinical human studies have shown that patients experiencing difficulty weaning from MV have impaired diaphragm performance, consistent with changes seen in VIDD models. Therefore, while there is growing evidence that MV rapidly leads to VIDD in animals and humans, and brief periods of diaphragm activity during MV support can lessen VIDD in a rodent model, there are no data examining strategies to attenuate this problem in humans. We have data examining human diaphragm gene expression (within subjects design) at the beginning and end of ~5 hours of surgery/MV support. The data revealed up regulation of several diaphragm genes controlling ubiquitin mediated catabolic activity and down regulation of genes critical to normal muscle contractile function. We propose to study the effects of periodically stimulating one hemidiaphragm and using the unstimulated hemidiaphragm as a control in a human MV/surgical model. The right or left hemidiaphragm will be stimulated via the corresponding phrenic nerve during surgery depending upon the ease of access. Costal diaphragm muscle samples will be obtained from each hemidiaphragm at the end of surgery. Gene expression, mitochondrial function and single muscle fiber contractile properties in the stimulated and unstimulated hemidiaphragms will be contrasted. This study will provide the first data examining the molecular and contractile effects of increased diaphragm activity during periods of MV/surgery in humans. The results from this research study will help direct efforts to develop rehabilitation interventions in the preoperative and postoperative period aimed at preventing VIDD in humans.

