[name] has observed vigorous left hemidiaphragm contractions on many occasions during temporary heart pacing when electrodes were applied to the pericardium close to the left phrenic nerve. Great care will be taken to ensure that the stimulating electrodes do not contact the phrenic nerve. The left phrenic nerve will be stimulated near the pulmonary artery to prevent pacing the heart. The right phrenic nerve will be stimulated on the right side of the pericardium.

Patients receive non-depolarizing neuromuscular blockers during surgery to prevent limb muscle contractions. The diaphragm is more resistant to neuromuscular blockade than limb muscles, and remains responsive to stimulation despite neuromuscular blockade sufficient to temporarily paralyze limb muscles (9, 10). The surgeon will select the hemidiaphragm for stimulation depending upon the ease of access to the corresponding phrenic nerve. There is no evidence that the muscle fiber contractile characteristics or gene expression differ between the right and left human hemidiaphragms.

Once the electrodes are sutured in place, the stimulator will be activated with the lowest possible current. The stimulator current will then be systematically increased until a vigorous contraction of the corresponding hemidiaphragm is observed, which will be

termed the threshold stimulus. The stimulus intensity will be adjusted to three times the threshold level for subsequent stimulation. The hemidiaphragm on the unstimulated side will be observed to verify that it is not entrained with the hemidiaphragm contractions on the stimulated side. Stimulation will be conducted for one minute (30 pulses per minute, 15 msec duration) either 30 or 60 minutes following initiation of MV and every 30 or 60 minutes thereafter. The frequency of stimulation (every 30 or 60 minutes) will be determined by the estimated duration of surgery. In order for both human hemidiaphragms to generate contractions, stimulation must be applied to both phrenic nerves or hemidiaphragms (11). The temporary wire electrodes that are used for the electrical stimulation will be removed at the end of the surgery.

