The method selected to obtain diaphragm biopsies was designed to minimize the risk of bleeding, phrenic nerve injury, or diaphragmatic impairment. The surgeon will obtain a full-thickness diaphragm sample, approximately 6 mm X 20 mm, from the antero-lateral costal regions of the stimulated and unstimulated hemidiaphragms, shortly before the surgery is completed. By harvesting the diaphragm biopsy from the anterior costal diaphragm, in a region opposite of the phrenic nerve insertion, we will minimize the proximity to phrenic insertion. The wounds will be closed with sutures. The surgeon will place the biopsy samples on ice and hand them to study staff. Tissue samples will be divided using the procedures described below. One part of the sample will be sent to [name]'s laboratory for mitochondrial respiration and gene analysis. One sample will be sent to [name] laboratory (University of Florida, College of Medicine) for RNA analysis. Samples to be analyzed with micro gene array and RNA analysis will be immediately placed in RNAlater solution and stored at -80° C until analysis. Another part of the sample will be sent to [name] laboratory (College of Health and Human Performance, University of Florida) for contractile and fiber type measures. Samples destined for single fiber contractile properties will be placed in a relaxing solution containing 50% glycerol (vol/vol) and stored at 20°C for no more than 4 wk before subsequent analysis. (12) A portion of the tissue samples will be sent to a non-UF investigator, [name] at the University of Arizona for

analysis of muscle titan integrity. After harvest, tissue samples will be coded to protect subject confidentiality and tissue samples will not contain identifying information such as the subject name, medical record are other identifying information. All of the tissue will be consumed during the analysis of the various variables and will not be stored or bank for use outside of this protocol.

In addition we will request the subject's permission to be videotaped for this research project. The process of stimulation of the phrenic nerve and the contraction or movement of the diaphragm muscle will be videotaped during the surgery. A separate consent [Consent to be videotaped and to different uses of the videotape(s)] will be obtained from the subjects.

C. After Surgery:

Data Analysis:

Microarray Analysis:

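### The stimulated side is chosen by ease of nerve access and not randomised, so wherever access differs, stimulation coincides with the more accessible side

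*Combined protocol and SAP*

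**What the plan says.** The selection rule appears three times. The Abstract says "The right or left hemidiaphragm will be stimulated via the corresponding phrenic nerve during surgery depending upon the ease of access". Section 6, Diaphragm stimulation, gives the decision to the surgeon ("This will be decided by the surgeon on the basis of ease of access to the corresponding phrenic nerve") and later repeats it: "The surgeon will select the hemidiaphragm for stimulation depending upon the ease of access to the corresponding phrenic nerve". No rule is given for patients in whom access is equal, and nothing is said about randomising, alternating or balancing sides.

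The unstimulated hemidiaphragm of the same patient is the control (Abstract). One biopsy per side is taken "from the antero-lateral costal regions of the stimulated and unstimulated hemidiaphragms, shortly before the surgery is completed" (Diaphragm Biopsies), and no start-of-surgery sample is described.

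Statistical Analysis plans a mixed model for single-fiber force, with a random subject intercept and fixed effects for stimulation and fiber type. Other outcomes get paired t tests or non-parametric tests. Neither analysis has a term for side or access.

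The stated reason for treating the sides as interchangeable is: "There is no evidence that the muscle fiber contractile characteristics or gene expression differ between the right and left human hemidiaphragms".

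**The concern.** Pairing removes differences between patients. It does not remove differences between the two sides of one patient. In a within-patient comparison, the way the side is allocated is what supports a causal reading, and here it follows a feature of the operative field.

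Two kinds of side difference could enter:

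- **More versus less accessible.** If tissue on the more accessible side differs at the end of surgery for reasons other than stimulation, that difference is added to the stimulation effect in every patient whose access differs.
- **Left versus right.** If one side is stimulated more often, part of any left-right difference is added too.

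All three aims in section 5 rest on this one contrast. Any such bias does not shrink as patients are added.

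**Working it through.** The plan gives no figure to reproduce. The only number is the ceiling of 100 subjects (section 6, Subjects), with no alpha, power, effect size or SD behind it. The structure can be worked out exactly; the sizes below are assumptions.

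**Structure.** Define, in SDs of the paired (stimulated minus unstimulated) difference:

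- t = the stimulation effect
- q = the share of patients whose access differs
- δ = the accessible-minus-other tissue difference in those patients
- p = the share stimulated on the left
- λ = the bias from a left-right difference if the left were always stimulated

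Under the access rule, the expected mean paired difference is t + qδ + (2p − 1)λ. If δ = λ = 0, as the plan in effect assumes, there is no bias. The λ term vanishes at p = 0.5; its multiplier (2p − 1) is 0.4 at 70/30 and 0.8 at 90/10. A yes/no indicator of being the more accessible side is collinear with stimulation wherever access differs. A three-level record (left easier, right easier, either acceptable) is not, provided some patients fall in the last group, but using it requires a constant stimulation effect across groups.

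**Illustration (a): accessible-side difference in every patient, t = 0.** Two-sided 5% paired t test, non-central t with df = n − 1 and non-centrality δ√n.

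| δ (assumed) | n = 20 | n = 50 | n = 100 |
|---|---|---|---|
| 0.1 SD | 7% | 11% | 17% |
| 0.2 SD | 14% | 28% | 51% |
| 0.3 SD | 25% | 55% | 84% |

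This is an upper case, because q = 1.

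**Illustration (b): surgeon indifferent in half the patients, 0.2 SD in the other half.** Simulated full-sample false-positive rates at n = 20 / 50 / 100.

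| Effect in the indifferent half | Surgeon's choice throughout | Indifferent half randomised | Bias (SD) |
|---|---|---|---|
| 0 | 7 / 11 / 17% | 7 / 11 / 17% | 0.10 → 0.10 |
| 0.1 SD | 10 / 18 / 32% | 7 / 10 / 16% | 0.15 → 0.10 |
| 0.2 SD | 14 / 28 / 51% | 7 / 11 / 16% | 0.20 → 0.10 |

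The randomised half taken alone has a 5% error rate in all three rows. If the effect there is zero, however, it has 5% without randomising as well. At 0.2 SD and n = 100 (50 patients in that half), the comparison is 28% unrandomised against 5% randomised.

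**Illustration (c): left-right difference λ = 0.3 SD.** Unadjusted rates at n = 20 / 50 / 100 are 4 / 4 / 4% at a 50/50 split, 7 / 12 / 20% at 70/30 and 17 / 37 / 65% at 90/10. With side coded +1/−1 they are 5% throughout. The price is a variance inflation of 1/(4p(1 − p)): 1/(4 × 0.7 × 0.3) = 1.19, and 1/(4 × 0.9 × 0.1) = 2.78. At 90/10, 100 patients then carry the information of 100/2.78 = 36.

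**Precision of a randomised subset of m patients.** The 95% CI half-width is t(0.975, m − 1)/√m: about 0.72 SD at m = 10, 0.41 at 25 and 0.28 at 50.

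These rates are for a single paired t test. They do not describe the mixed model or the array analysis.

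**The case against.** The case for the plan is substantial. Choosing a nerve for its accessibility makes it the accessible one by definition; bias also requires the costal muscle on that side to differ for another reason, and the documents name no mechanism. Access concerns the nerve on the pericardium, while both biopsies come from the same antero-lateral costal region. The left and right electrode sites differ ("The left phrenic nerve will be stimulated near the pulmonary artery to prevent pacing the heart"), but the stimulus is scaled to the observed response: "The stimulus intensity will be adjusted to three times the threshold level for subsequent stimulation". The left-right question is addressed for contractile properties and gene expression, two of the three aims. Randomising also cannot reach patients in whom only one nerve is acceptable, where an accessible-side difference is most plausible.

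Most of this stands, and it limits the weight of the point. It does not remove it. The protocol's statement reports absence of evidence and concerns left versus right, not more versus less accessible in a given operation. It does not cover mitochondrial function (Aim 3).

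A reader might infer that the comparison is biased, or that its error rate is as high as the tables show. The documents do not support that: they give neither a size for any side difference nor the frequency of unequal access. A reader might also infer from "will be impaneled before any additional subjects are studied" that patients have already been stimulated under this protocol. That is possible, but the wording could refer to the completed five-subject study described in section 7.

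**Conclusion.** The point holds as a gap in allocation and analysis. Side is set by access, there is no per-side baseline, and no planned model includes side. Stimulation is therefore inseparable from relative accessibility wherever access differs, and is mixed with left-right differences if the split is unequal. That much follows from the text.

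Whether any bias results is unknown. The error rates rest entirely on assumed effects, shares and splits, and should not set the severity. It is also tempting to conclude that randomising where possible would repair the whole study. It would not: the resulting estimate is unbiased only for the randomised patients. The full-sample bias falls only to the extent that an accessible-side effect exists in those patients. The point should be addressed, with medium confidence, because the gap is certain, its consequence is not, and most of the remedy is cheap.

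**What to change.** 1. **Allocation, for patients still to be studied.** Before the allocation is revealed, the surgeon records whether the left nerve is easier, the right nerve is easier, or either is acceptable. Where either is acceptable, take the side from a pre-generated concealed list balanced for left and right. Otherwise the surgeon's choice stands, and the surgeon may override at any time. Report the randomised subset alongside the full sample, as unbiased for those patients only.
2. **Recording and sensitivity analysis, for all patients.** Record side, procedure and reason. Regress the paired difference on side coded +1/−1, so that the intercept is the stimulation effect; add left/right as a fixed effect to the mixed model; and report results by side. This removes left-right bias only.
3. **Limitation.** State that accessible-side confounding remains in patients who were not randomised.

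The cost is a short amendment, a concealed list, a few data fields and one sensitivity model. No biopsy or stimulation is added, but the list will sometimes direct electrodes to a nerve the surgeon accepts but might not have picked. The randomised subset may be small, since the documents do not say how often either nerve is acceptable. Randomising improves on simply recording access only if an accessible-side effect exists in those patients. The side term costs precision when the split is uneven and cannot be estimated if one side is always used. Anyone already studied can only have side and reason recorded.
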